4.2 Definition of Dose-Limiting Toxicity (DLT) and Criteria for Dose Escalation

DLT in a given patient is defined as any grade III non-hematologic (thought to be MX related) or IV non-hematological toxicity or any grade IV anemia, neutropenia or thrombocytopenia lasting greater than 7 days, that is felt to be related to MX or the MX + TMZ drug combination occurring during the first cycle of treatment.

MTD (maximum tolerated dose) will be defined based on the toxicities observed during the first cycle of treatment

Definition of MTD: The MTD is defined as the highest dose tested in which none or only one patient experienced DLT attributable to the study drug combination, when at least six patients were treated at that dose and are evaluable for toxicity. The MTD is one dose level below the highest dose tested in which 2 or more patients experienced DLT attributable to the study drug. At least 6 patients will be treated at the MTD.

Management and dose modifications associated with the above adverse events are outlined in Section 5.

Special consideration is given to the evaluation of neurologic toxicity given the animal toxicity data and CNS involvement of a proportion of eligible patients.

Specifically:

- all patients will be evaluated by a staff Neurologist prior to initiation of treatment
- patients will undergo frequent (every 4-8 hours) neurologic checks by a CRU RN during the 1-day inpatient CRU stay on the first day of treatment.
- Patients will be evaluated by the covering Oncology clinician during the 1-day inpatient CRU stay on cycle 1.

A neurology consult will be obtained for any observed treatment-related neurologic toxicity \geq grade 2. For patients enrolled in cohort B (patients with CNS disease) with pre-existing neurologic toxicity cleared for participation by the neuro-oncology team, a neuro-oncology or neurology consult will be obtained for any observed treatment-related worsening in neurologic toxicities.

Dose escalation will proceed within each cohort according to the following scheme. DLT is defined above.

Number of Patients with DLT at a Given Dose Level	Escalation Decision Rule
0 out of 3	Enter 3 patients at the next dose level.
≥ 2	Dose escalation will be stopped. This dose level will be declared the maximally administered dose (highest dose administered). Three (3) additional patients will be entered at the next lowest dose level if only 3 patients were treated previously at that dose.
1 out of 3	
Enter at least 3 more patients at this dose level.
 
 • If 0 of these 3 patients experience DLT, proceed to the next dose level. • If 1 or more of this group suffer DLT, then dose escalation is stopped, and this dose is declared the maximally administered dose. Three (3) additional patients will be entered at the next lowest dose level if only 3 patients were treated previously at that dose. 
 ◦ As of protocol v22, if 1/3 patients experience any DLT that is not of a CNS nature in Cohort B dose level 6, we will continue dose escalation to dose level 7 since we have already treated three subjects in Cohort A dose level 6 and seven subjects in Cohort A dose level 7, none of whom experienced non-CNS toxicities
≤ 1 out of 6 at highest dose level below the maximally administered dose	This is generally the recommended phase 2 dose. At least 6 patients must be entered at the recommended phase 2 dose.

Cohort A, Dose level 1: Dose level 1 of Cohort A will be expanded to 10 evaluable patients. Further dose escalation will occur only if less than 4 out of the 10 patients experience a DLT. Enrollment to subsequent dose levels will follow the rules outlined in Sec. 4.1.

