Other Agent: Temozolomide, commercially available

SCHEMA

Cycle 1 and subsequent cycles.

Methoxyamine (MX) will be given as a single one hour infusion every 28 days.

Temozolomide (TMZ) will be given orally for 5 days every 28 days on days 1-5. It will be administered within five minutes of initiation of methoxyamine

Cycles are concluded every 28 days.

Week1	Day1	2	3	4	5
MX	↔				
TMZ	↓	↓	↓	↓	↓

Note:

Treatment toxicities for cycle 1 will be considered for dose limiting toxicity (DLT) attribution. Dose modifications are allowed for cycle 2 and beyond.

Cohort A (eligible patients with no CNS disease)

DOSE-ESCALATION SCHEDULE		
Dose Level	Dose	
	TMZ (mg/m ² /day) x 5days	MX (mg/m ²)
Level -1	100	15
Level 1	150	15
Level 2	150	30
Level 3	150	60
Level 4	150	90
Level 5	150	120
Level 6	150	150
Level 7	200	150

Cohort B (eligible patients with CNS disease)

DOSE-ESCALATION SCHEDULE		
Dose Level	Dose	
	TMZ (mg/m ² /day) x5days	MX (mg/m ²)
Level -1	75	15
Level 1	100	15
Level 2	150	15

Level 3	150	30
Level 4	150	60
Level 5	150	120
Level 6	150	150
Level 7	200	150

For each cohort, 3 patients will be entered sequentially to each dose level.

- If none of the 3 patients at a dose level experience dose limiting toxicity (DLT) during the first cycle, new patients may be entered at the next dose level.
- If 1/3 patients experiences DLT during the first cycle, up to 3 more patients will be treated at the same dose level. If the 1st patient in the expanded cohort (4th at the given DL), experiences no DLT, then the remaining 2 patients can start treatment without a necessary delay.
 - As of protocol v22, if 1/3 patients experience any DLT that is not of a CNS nature in Cohort B dose level 6, we will continue dose escalation to dose level 7 since we have already treated three subjects in Cohort A dose level 6 and seven subjects in Cohort A dose level 7, none of whom experienced non-CNS toxicities
- If 2 or more experience DLT during the first cycle, no further patients are started at that dose and the MTD is the highest dose level in which <2 (of 6) patients develop DLT.
- If the final dose level is deemed the MTD, 6 patients will be treated at this dose level, even if a DLT has not been observed.

Select non-hematologic grade 3 or 4 or hematologic grade 4 drug-related toxicities (CTC version 3.0) occurring in the first 28 days of study will be considered a DLT.

TABLE OF CONTENTS

	Page
SCHEMA	4
1. OBJECTIVES	7
2. BACKGROUND	7
3. PATIENT SELECTION	11

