4.1 Agent Administration

For all cycles, TMZ will be given orally for 5 days every 28 days. MX will be given as a single one-hour IV infusion every 28 days. Temozolomide will be administered within 5 minutes following the initiation of methoxamine.

Patients will be treated and monitored in the inpatient setting (Clinical Research Unit) during MX administration (on cycle 1 day 1). A physician will be onsite within the hospital in case an adverse event occurs.

Cohort A (eligible patients with no CNS disease)

DOSE-ESCALATION SCHEDULE		
Dose Level	Dose	
	TMZ (mg/m ² /day) x5days	MX (mg/m ²)
Level -1	100	15
Level 1	150	15
Level 2	150	30
Level 3	150	60
Level 4	150	90
Level 5	150	120
Level 6	150	150

Level 7	200	150
---------	-----	-----

Cohort B (eligible patients with CNS disease)

Dose Level	DOSE-ESCALATION SCHEDULE	
	Dose	
	TMZ (mg/m ² /day) x5days	MX (mg/m ²)
Level -1	75	15
Level 1	100	15
Level 2	150	15
Level 3	150	30
Level 4	150	60
Level 5	150	120
Level 6	150	150
Level 7	200	150

For each cohort, 3 patients will be entered sequentially to each dose level.

- If none of the 3 patients at a dose level experience dose limiting toxicity (DLT) during the first cycle, new patients may be entered at the next higher dose level.
- If 1/3 patients experience a DLT during the first cycle, up to 3 more patients will be treated at the same dose level. If the 1st patient in the expanded cohort (4th at the given DL), experiences no DLT, then the remaining 2 patients can start treatment without a necessary delay.
 - As of protocol v22, if 1/3 patients experience any DLT that is not of a CNS nature in Cohort B dose level 6, we will continue dose escalation to dose level 7 since we have already treated three subjects in Cohort A dose level 6 and seven subjects in Cohort A dose level 7, none of whom experienced non-CNS toxicities
- If 2 or more experience DLT during the first cycle, no further patients are started at that dose and the MTD is the highest dose level in which <2 (of 6) patients develop DLT.
- If the final dose level is deemed the MTD, 6 patients will be treated at this dose level even if a DLT has not been observed.

Select non-hematologic grade 3 or 4 or hematologic grade 4 drug-related toxicities (CTC version 3.0) occurring within the first 28 days of the study will be considered a DLT.

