Cohort A, Dose level 1: Two DLTs were observed in Dose Level 1 of Cohort A: grade 3 psychosis and grade 3 allergic reaction. Upon further review of the hypersensitivity reaction, it is believed that this was an idiosyncratic event, and further expansion of this

dose level is warranted. Dose level 1 of Cohort A will be expanded to 10 evaluable patients. Further dose escalation will occur only if less than 4 out of the 10 patients experience a DLT. Enrollment to subsequent dose levels will follow the rules outlined above.

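### The Schema and Section 4.1 word the DLT criterion differently from Section 4.2, and the protocol says neither which governs nor how a grade 4 cytopenia still open at day 28 is counted

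*Combined protocol and SAP*

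**What the plan says.** Section 4.1 closes its escalation rules with a DLT criterion of its own: "Select non-hematologic grade 3 or 4 or hematologic grade 4 drug-related toxicities (CTC version 3.0) occurring within the first 28 days of the study". The Schema has almost the same sentence: "Select non-hematologic grade 3 or 4 or hematologic grade 4 drug-related toxicities (CTC version 3.0) occurring in the first 28 days of study". Neither gives a minimum duration, names cell lines, lists what 'select' covers, or points to Section 4.2.

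Section 4.2 is headed as the definition of DLT. It counts any grade IV non-hematologic toxicity, grade III non-hematologic toxicity thought to be due to methoxyamine (MX), and "any grade IV anemia, neutropenia or thrombocytopenia lasting greater than 7 days, that is felt to be related to MX" or to the combination of MX and temozolomide (TMZ), in cycle 1. It introduces its decision table with "Dose escalation will proceed within each cohort according to the following scheme. DLT is defined above". It ties the MTD to the same count: "The MTD is defined as the highest dose tested in which none or only one patient experienced DLT attributable to the study drug combination", given at least six evaluable patients. After the table, its paragraph on Cohort A level 1 sends the reader back to the 4.1 rules for later levels.

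Two levels have their own rule. At Cohort A level 1, expanded to ten patients, "Further dose escalation will occur only if less than 4 out of the 10 patients experience a DLT". At Cohort B level 6, the v22 amendment added this: "if 1/3 patients experience any DLT that is not of a CNS nature in Cohort B dose level 6, we will continue dose escalation". The next level there is level 7. The reason given is the experience of three subjects at Cohort A level 6 and "seven subjects in Cohort A dose level 7, none of whom experienced non-CNS toxicities".

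**The concern.** The DLT count is the only input to the escalation decisions and to the MTD, which is the first objective. A colleague working from the Schema or 4.1 and another working from 4.2 could classify the same patient differently, and with three to six patients per level one patient can decide the outcome. The protocol also does not say which wording was applied to patients already treated. That matters for the v22 rule if its statement about Cohort A levels 6 and 7 refers to DLTs.

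A second, smaller gap sits inside 4.2. It sets a duration test of more than 7 days but does not say whether the episode must only start in cycle 1 or must also pass 7 days within it. Nor does it say whether escalation waits for an episode still open at day 28.

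**Working it through.** **1. The plan's own table.** Under the standard rule, P(escalate) = (1−p)³ + 3p(1−p)⁵. At p = 0.1, 0.2, 0.3, 0.4 and 0.5 this gives 0.906, 0.709, 0.494, 0.309 and 0.172. Section 12 states 0.91, 0.71, 0.49, 0.32 and 0.17. The table reproduces, apart from a difference of 0.01 at p = 0.4. It takes p as given; the open question is which events make up p.

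**2. The two wordings side by side.**

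| Element | Schema and 4.1 | 4.2 |
|---|---|---|
| Non-hematologic | 'Select' grade 3 or 4, no list | Any grade IV; grade III if thought MX related |
| Hematologic | Grade 4, no cell lines named | Grade IV anemia, neutropenia or thrombocytopenia |
| Duration | None stated | More than 7 days |
| Attribution | Drug-related | MX, or MX with TMZ |
| Window | First 28 days | First cycle (28 days) |

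The result depends on what 'select' modifies.
- If it modifies only the non-hematologic half, a drug-related grade 4 neutropenia of 3 days is a DLT under 4.1 and not under 4.2. The same holds for a drug-related grade 4 lymphopenia, which is not among the three cytopenias in 4.2. It may hold for a cytopenia blamed on TMZ alone.
- If it modifies both halves, 4.1 announces a subset that 4.2 may be supplying, and those examples need not conflict.

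**3. What one reclassified patient changes.**
- Standard 3+3 levels: 0/3 (escalate) becomes 1/3 (expand), or 1/6 becomes 2/6 (stop).
- Cohort B level 6 under v22: one non-CNS DLT in three still escalates, so a disputed cytopenia matters only between 1/3 and 2/3.
- Cohort A level 1: it matters only between 3 and 4 of 10.
- Cohort B level 7: there is no further escalation, but it can decide whether at most 1 of 6 is met.

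**4. Illustration of size.** Let s be the non-hematologic DLT rate (assumed 0.10, with 'select' taken to capture all of it), h the cycle 1 grade 4 cytopenia rate, and f the share of those cytopenias that counts. Then p = 1 − (1−s)(1−f·h). Section 6.1.8 gives TMZ-alone rates at age 70 or under: neutropenia 62/871 = 0.0712 and thrombocytopenia 48/879 = 0.0546. So h runs from 0.0712 (full overlap) to 0.1258 (none). The case f = 1 is 4.1 with 'select' confined to the non-hematologic half. Under 4.2, f lies anywhere from 0 to 1; one half is an assumption.

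| Share counted | p | Standard 3+3: escalate | Cohort B level 6, v22: P(0 or 1 of 3) | Cohort B level 7: P(0 or 1 of 6) |
|---|---|---|---|---|
| None | 0.100 | 0.906 | 0.972 | 0.886 |
| Half | 0.132–0.157 | 0.849–0.800 | 0.952–0.934 | 0.818–0.761 |
| All | 0.164–0.213 | 0.785–0.680 | 0.928–0.883 | 0.743–0.623 |

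The v22 column assumes that every DLT is non-CNS. Varying s, the standard 3+3 figure is 0.973 (none) against 0.876–0.774 (all) at s = 0.05, and 0.709 against 0.585–0.493 at s = 0.20.

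**5. Timing.** If more than 7 days had to elapse within cycle 1, an episode starting on day 22 would have reached 28 − 22 + 1 = 7 days at day 28, which is not more than 7. Day 21 would be the last qualifying onset. Section 6.1.8 puts the median TMZ nadirs at day 26 (platelets) and day 28 (neutrophils). Those are nadirs of any depth, so they do not show how often a grade 4 episode starts that late.

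**The case against.** The strongest reply is that there is one definition and one loose summary. Section 4.2 has the heading, the defining sentence and the pointer above its decision table. Section 4.1 is about agent administration, and 'select' can grammatically govern the whole phrase. This makes 4.2 the likelier governing text. It does not settle the matter: neither the Schema nor 4.1 refers to 4.2, both state an operative criterion, and 4.2 sends readers back to the 4.1 rules. 'Select' is also an odd summary of a definition that takes any grade IV non-hematologic toxicity.

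A reader might infer that 4.1 makes every grade 4 hematologic event a DLT whatever its duration. The text does not say that; it is silent on duration, and 'select' may narrow that half too.

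A reader might also infer that late cytopenias will go uncounted. The documents do not support this. An event occurring in cycle 1 most naturally means onset in cycle 1. Section 8 schedules blood counts in every week of cycle 1 and at the start of later cycles. Section 5 requires neutrophils and platelets to recover before the next cycle, with holds of up to 2 weeks. Duration can therefore usually be established. What is missing is a sentence on classification and on whether escalation waits.

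Finally, it may be said that nothing has gone wrong. The only DLTs named are non-hematologic (grade 3 psychosis and grade 3 allergic reaction, Cohort A level 1). Cohort A has already treated patients at levels 6 and 7, so its lower-level escalations are past. Both points stand. They limit the consequence but do not reconcile the texts.

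**Conclusion.** The inconsistency is real and should be resolved before an MTD is declared. The Schema and 4.1 differ from 4.2 on duration, cell lines, breadth of non-hematologic events and attribution, and no statement says which applies. Whether a given cytopenia is classified differently depends on how 'select' is read. On the narrower reading of that word, one patient can change a decision at levels run under the standard 3+3 rule; the reach is smaller at Cohort B level 6 and Cohort A level 1.

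The probabilities are illustrative. They rest on an assumed background rate, on cytopenia rates for TMZ rather than the combination, and on durations, overlap and attribution that the documents do not give. The shift is zero if every grade 4 cytopenia counts under both texts. The figure for at most 1 of 6 applies to Cohort B level 7 only, since Cohort A level 7 has seven treated patients.

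It would be wrong to conclude that past escalations were mistaken. No disputed event appears in the documents. Read literally, the v22 statement that Cohort A levels 6 and 7 saw no non-CNS toxicities leaves no cytopenia in dispute there. If DLTs were meant, the definition behind that count is not stated. The Section 12 arithmetic is not in question.

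**What to change.** - Reconcile the Schema, 4.1 and 4.2 into one DLT definition covering events, cell lines, duration and attribution. The choice is the sponsor's. Make the Schema and 4.1 refer to it.
- In that definition, state whether the more-than-7-days test applies by onset in cycle 1, and how an episode still open at day 28 is counted for the escalation decision.
- Before declaring an MTD, re-review from data on file only those cycle 1 events whose DLT status differs between the two wordings. If there are none, record that.
- State which definition underlies the v22 statement on Cohort A levels 6 and 7.

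The cost is amendment wording and a limited re-review, with no new visits or tests. The downside is that a recorded DLT count may change.

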1. OBJECTIVES

- 1.1 To determine the maximum tolerated dose of methoxyamine given in conjunction with temozolomide in patients with and without CNS disease.
- 1.2 To determine the dose limiting toxicities of the combination of methoxyamine and temozolomide in patients with and without CNS disease.
- 1.3 To determine the pharmacokinetics of these two agents when given alone or in combination, as well as the pharmacokinetic profile of methoxyamine after a single one-hour IV administration.
- 1.4 To determine relative DNA damage, as single or double strand breaks by comet assay in blood mononuclear cells which will serve as a surrogate for tumor response to the drug combination.

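### Level 6 to 7 raises only temozolomide, yet section 4.2 does not count first-cycle toxicity attributed to temozolomide alone as a DLT

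*Combined protocol and SAP*

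**What the plan says.** Section 4.2 requires a first-cycle toxicity to be one "that is felt to be related to MX or the MX + TMZ drug combination occurring during the first cycle of treatment". Within that, the non-hematologic criterion is "any grade III non-hematologic (thought to be MX related) or IV non-hematological toxicity", so grade 3 events carry a further condition that names MX only. Hematologic DLTs are grade 4 cytopenias lasting more than 7 days. The escalation table relies on this definition: "Dose escalation will proceed within each cohort according to the following scheme. DLT is defined above".

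The MTD sentences in section 4.2 use two other descriptions. One defines the MTD as the "highest dose tested in which none or only one patient experienced DLT attributable to the study drug combination", with at least six evaluable patients. The next reads "The MTD is one dose level below the highest dose tested in which 2 or more patients experienced DLT attributable to the study drug". Section 4.1 and the Schema refer to selected drug-related toxicities without an MX limit, but do not list which ones.

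In the dose tables for both cohorts, level 6 is TMZ 150 mg/m²/day with MX 150 mg/m², and level 7 is TMZ 200 with MX 150. Level 7 is the last level. The v22 text says that "if 1/3 patients experience any DLT that is not of a CNS nature in Cohort B dose level 6, we will continue dose escalation" to level 7. It justifies this by the three Cohort A subjects at level 6 and seven at level 7, who are said to have had no non-CNS toxicities.

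Objective 1.1 is "To determine the maximum tolerated dose of methoxyamine given in conjunction with temozolomide in patients with and without CNS disease".

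**The concern.** A DLT filter centred on MX fits the objective while MX is the drug that rises. At level 6 to 7 it does not. The step tests a higher TMZ dose, and an event that the investigator ascribes to TMZ alone is outside the definition that judges the step. For grade 3 non-hematologic events, even attribution to the combination may not satisfy the MX-only condition.

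At stake is whether TMZ 200 / MX 150 is declared the MTD. This matters most for Cohort B level 7, which the v22 text treats as still ahead. That text allows escalation after a non-CNS DLT in one of three patients at Cohort B level 6, so the level 7 count carries more of the non-CNS check.

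**Working it through.** **1. Which definition governs.** The escalation table points to the section 4.2 definition. Section 4.1 and the Schema give no list of the selected toxicities, so they cannot be applied alone and read as summaries. Under section 4.2:

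| First-cycle event attributed to TMZ alone | Counted? |
|---|---|
| Grade 3 non-hematologic | No: neither the MX condition nor the general clause is met |
| Grade 4 non-hematologic | No: general clause not met |
| Grade 4 cytopenia over 7 days | No: general clause not met |

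The last two rows are counted if the event is ascribed to the combination. For the first row that is uncertain. The exposure is therefore chiefly grade 3 non-hematologic; this is an inference, not a statement in the protocol.

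**2. What the step changes.** Level 6 to 7: TMZ 150 to 200 (200/150 = 1.33); MX 150 to 150.

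**3. The plan's own figures.** For the 3+3 rule in section 12, P(escalate) = (1−p)³ + 3p(1−p)²·(1−p)³. At p = 0.2 this is 0.512 + 0.197 = 0.709. At p = 0.1 to 0.5 it gives 0.906, 0.709, 0.494, 0.309 and 0.172, against the printed 0.91, 0.71, 0.49, 0.32 and 0.17. The table reproduces, apart from a rounding slip at 0.4. Its rate p is the rate of counted events, so TMZ-only events lie outside it.

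**4. How the decision can turn.** Level 7 is the MTD with 0 or 1 patients with DLT in six. With one scored DLT plus one set-aside event in another patient, section 4.2 gives 1 of 6 (MTD). Counting the second event gives 2 of 6 (not MTD). No assumed rate is needed for this.

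**5. Illustration of size.** Let q be the scored DLT rate and t the rate of otherwise qualifying TMZ-only events. The protocol gives neither; both are assumed, and independent. The total rate is p = 1 − (1−q)(1−t), and P(at most 1 of 6) = (1−p)⁶ + 6p(1−p)⁵. For q = 0.15 and t = 0.02: p = 1 − 0.85 × 0.98 = 0.167, giving 0.334 + 0.402 = 0.736.

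| q | t = 0 | t = 0.01 | t = 0.02 | t = 0.05 |
|---|---|---|---|---|
| 0.10 | 0.886 | 0.868 | 0.849 | 0.788 |
| 0.15 | 0.776 | 0.756 | 0.736 | 0.674 |
| 0.20 | 0.655 | 0.636 | 0.616 | 0.558 |

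The fall is about 0.02, 0.04 and 0.10 at the three non-zero rates, and zero at t = 0. Given exactly one scored DLT in six, the chance of at least one set-aside event among the other five is 1 − (1−t)⁵ = 0.049, 0.096 and 0.226.

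**The case against.** The strongest reply is that an MX-centred rule is a legitimate choice for objective 1.1. MX is 150 mg/m² at both levels, so choosing between them does not change the MX dose. That stands and limits the stakes to the TMZ partner dose. A reader might infer that the MX MTD itself is in doubt; the dose tables do not support that.

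Second, TMZ-only is not a recorded category. Section 10.2 grades relation to study treatment, section 10.3 to study agents, and TMZ is given within five minutes of starting MX. Many events would be scored to the combination. The rat data in section 6.2.3, where neutropenia on TMZ worsened as the MX dose rose, point that way for cytopenias. The Appendix B abstract, which reports grade 1–2 nausea and vomiting on MX with TMZ, points that way for gastrointestinal events. This also stands: it narrows the gap, and it means a retrospective list may not be recoverable. It does not close the gap, because section 4.2 still asks for an MX or combination judgement.

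Third, section 5 holds the next cycle until drug-related grade 3 non-hematologic toxicity recovers to grade 2, and reduces the dose after grade 4 hematologic toxicity. Section 10.4 adds committee review. A reader might infer that patients are unprotected; they are not. But these provisions do not alter the DLT count.

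Two further inferences fail. The blank gastrointestinal and hepatobiliary rows in the section 10.1.1.1 table do not show that such events would be ascribed to TMZ, because its introduction covers MX and/or TMZ. Nor can the 10% and 6% severe nausea and vomiting figures in section 6.1.8 serve as t: they are not stated as first-cycle, mix grades 3 and 4, and are not rates of events that an investigator here would ascribe to TMZ alone. Hepatic injury is described there as rare.

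**Conclusion.** The point holds as a mismatch between the DLT definition and one escalation step. As written, toxicity attributed to the only drug being raised does not count against level 7, and one such event can decide the MTD call when there is already one scored DLT in six.

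The size is unknown and may be zero. The falls of 0.02 to 0.10 rest on assumed TMZ-only rates of 1–5%, assumed scored DLT rates of 10–20%, and independence.

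A reader might also infer that events have already been set aside at Cohort A level 7. The protocol does not show that: read literally, the v22 text says the seven subjects had no non-CNS toxicities. Zero of seven is weak evidence about the underlying rate (one-sided 95% upper bound 1 − 0.05^(1/7) = 0.35), but it gives no sign of a missed event. The practical exposure is Cohort B level 7.

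**What to change.** - **Cohort B level 7, prospectively:** keep the section 4.2 grade, 7-day and relatedness criteria. Delete the bracketed MX condition on grade 3 non-hematologic events. Extend the attribution clause to *related to MX, TMZ or the MX + TMZ combination*.
- **One definition:** have section 4.1, the Schema and the two MTD sentences refer to this definition.
- **Cohort A level 7:** report any first-cycle event set aside as TMZ-only where the records allow, or state that none was found. Do not re-score lower levels, including Cohort B level 1 to 2, which also raised only TMZ.

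No dose changes. The cost is one wording amendment and a short attribution check on seven Cohort A subjects. The downside is that level 7 is somewhat less likely to be declared the MTD if such events occur. Its DLT definition would also be broader than that used at earlier levels, and the report should say so.

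### The second sentence of the Section 4.2 MTD definition puts no DLT limit on the level it names, so after backfill it can name a level that the protocol's other MTD statements reject

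*Combined protocol and SAP*

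**What the plan says.** Section 4.2 gives two MTD sentences in a row. The first takes the "highest dose tested in which none or only one patient experienced DLT attributable to the study drug combination", provided at least six evaluable patients were treated there. The second says: "The MTD is one dose level below the highest dose tested in which 2 or more patients experienced DLT attributable to the study drug". The sentence that follows adds a patient count only: "At least 6 patients will be treated at the MTD".

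Three other statements carry the first sentence's limit:

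- The Schema and Section 4.1 both say "the MTD is the highest dose level in which <2 (of 6) patients develop DLT".
- The last row of the Section 4.2 decision table gives the recommended phase 2 dose as the level with at most "1 out of 6 at highest dose level below the maximally administered dose", qualified by the word generally.

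Two operating rules matter here. When a level fails, the decision table backfills the level below: "Three (3) additional patients will be entered at the next lowest dose level if only 3 patients were treated previously at that dose". As of version 22, one level has its own exception (Schema, Sections 4.1 and 4.2): "if 1/3 patients experience any DLT that is not of a CNS nature in Cohort B dose level 6, we will continue dose escalation" to level 7.

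Section 12 tabulates the probability of escalating at true DLT rates 0.1 to 0.5. Its second row treats not escalating as the same thing as the prior level being the MTD, and the text below attaches a 29% chance to that outcome at a 20% DLT rate. Neither states which levels the table covers.

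**The concern.** Finding the MTD is objective 1.1. A level that escalated on 0/3 has only three patients, so the protocol sends three more there once the next level fails. Those patients can have DLTs. If two or more do, the lower level stands at 2 or 3 DLTs in 6. The second sentence still names it, because it looks only at the level above. The other four statements reject it. The same counts then give one level under one sentence and a lower level, or none, under the other, and the choice would be made after the data are seen.

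The version 22 exception adds a second way to get there at Cohort B level 6. That level can escalate carrying one non-CNS DLT in three, so a single further DLT in the backfill is enough. The text does not say how such a level is judged after backfill.

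**Working it through.** **Inputs.** DLT rates p = 0.1 to 0.5 and the printed escalation probabilities come from Section 12. The escalation and backfill rules come from Sections 4.1 and 4.2. Assumptions: DLTs are independent, p is constant within a level, and backfill is completed to 6. The share f of DLTs that are CNS events is not given, so it is taken over its whole range. Write q = 1 − p.

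**1. The plan's own figure.** Ordinary 3+3 escalates on 0/3, or on 1/3 followed by 0/3:

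P(escalate) = q³ + 3pq²·q³ = 0.906/0.709/0.494/0.309/0.172

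Section 12 prints 0.91/0.71/0.49/0.32/0.17. It therefore describes ordinary 3+3 levels. The entry at 0.4 should be 0.31 (and 0.69 in the second row), a small slip.

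**2. An example of the split.** Suppose level 4 has 2/3, level 3 passed on 0/3 and ends at 2/6 after backfill, and level 2 has 1/6. The first sentence names level 2 and the second names level 3. If instead the level below the failed one ends at 1/6, both sentences name it.

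**3. Ordinary 3+3.** Only a level that passed on 0/3 is backfilled; one that passed on 1/3 then 0/3 already has 1/6. So

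J = P(escalates and ends with 2 or more DLTs in 6) = q³ · P(Bin(3,p) ≥ 2)

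At p = 0.3: 0.343 × 0.216 = 0.074. Given escalation: 0.074 / 0.494 = 0.150. With independence, conditioning on failure of the next level leaves this unchanged.

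**4. Cohort B level 6 under version 22.** A first-three result of 1/3 with a non-CNS DLT also escalates:

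P(escalate) = q³ + 3pq²·[(1 − f) + f·q³]

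J = q³ · P(Bin(3,p) ≥ 2) + 3pq²·(1 − f)·(1 − q³)

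At p = 0.3 and f = 0: J = 0.074 + 0.441 × 0.657 = 0.364; P(escalate) = 0.784; ratio 0.464. With f = 1 both formulas reduce to the ordinary ones.

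**5. Joint probability for Cohort B levels 6 and 7.** Level 7 is the last level, and Section 4.1 says "If the final dose level is deemed the MTD, 6 patients will be treated at this dose level", so it fails with probability P(Bin(6,p₇) ≥ 2). If p₇ = p (assumption), this is 0.114/0.345/0.580/0.767/0.891. The joint probability is J times this; at p = 0.3 and f = 0, 0.364 × 0.580 = 0.211. It starts from level 6 having been opened.

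| True DLT rate | 0.1 | 0.2 | 0.3 | 0.4 | 0.5 |
|---|---|---|---|---|---|
| Conditional: ordinary 3+3, or level 6 if all DLTs CNS | 0.02 | 0.08 | 0.15 | 0.25 | 0.36 |
| Conditional: level 6, half CNS | 0.06 | 0.18 | 0.34 | 0.51 | 0.67 |
| Conditional: level 6, none CNS | 0.09 | 0.27 | 0.46 | 0.64 | 0.78 |
| Joint, levels 6 and 7, all CNS | 0.00 | 0.02 | 0.04 | 0.06 | 0.06 |
| Joint, half CNS | 0.01 | 0.05 | 0.13 | 0.19 | 0.20 |
| Joint, none CNS | 0.01 | 0.08 | 0.21 | 0.32 | 0.35 |
| P(escalate) from level 6, none CNS | 0.97 | 0.90 | 0.78 | 0.65 | 0.50 |

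Conditional means given that the level escalated and the next one failed. The last row shows how far the Section 12 table can be from Cohort B level 6 under version 22.

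**The case against.** The best reply is that the governing limit is already stated four times. Only the first sentence is framed as the definition, and the second can be read as the usual 3+3 corollary of it. A reader applying the whole paragraph would not pick a level with 2/6. The procedure is not silent either: the decision-table row for 2 or more DLTs has no denominator and could be applied again to a backfilled level, although its description of that level as the highest administered fits poorly. This largely stands, and it limits the severity. It does not remove the fault. The second sentence sits inside the definition of the MTD, is worded as a rule, and returns a different level from the other statements on patterns that the protocol's own backfill produces. Section 12 repeats the unconditional version.

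Three stronger readings are tempting and are not supported.

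- A reader might infer that Cohort A already shows the conflict, because level 1 has two DLTs on record and the second sentence would point below it. That needs no higher Cohort A level to have 2 or more DLTs, which is not reported. It also disappears if the sentence means one level below the maximally administered dose, the term the decision table uses.
- A reader might infer that version 22 makes a wrong MTD likely at Cohort B level 6. Any increase depends wholly on DLTs being non-CNS, and the documents give no such share. If all are CNS events, the exception adds nothing.
- A reader might infer that the Section 12 table is wrong throughout. It reproduces the ordinary 3+3 rule apart from one rounding slip; what it lacks is a statement of scope and a condition on its second row.

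**Conclusion.** Wrong as written, with minor to moderate severity. The second MTD sentence omits the limit of at most 1 DLT in 6 and can name a level that the other four statements reject. At true DLT rates of 0.2 to 0.3, the chance of this, given escalation and failure of the next level, is 0.08 to 0.15 under ordinary 3+3. At Cohort B level 6 it lies between those values and 0.27 to 0.46, depending on the unknown CNS share. The joint probability for Cohort B levels 6 and 7 at the same rates runs from 0.02 to 0.04 (all CNS) up to 0.08 to 0.21 (none CNS), if both levels share one rate. The outcome at those levels is not reported, so these figures show how often the wording could matter, not that it has.

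**What to change.** Reconcile the Schema and Sections 4.1 and 4.2 so that one MTD definition returns a single level, or states that no MTD is established, for any DLT pattern. It should say whether the level below a failed one must meet the limit after backfill, what follows if it does not, and how a Cohort B level 6 that escalated on 1/3 is judged after backfill. No view is taken here on which escalation rule or dose is right.

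In Section 12:

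- State that the table covers levels run under the ordinary 3+3 rule.
- Relabel the second row as not escalating, with the prior level being the MTD only if it meets the MTD definition.
- Amend the 29% sentence to match.
- Correct the 0.4 column to 0.31 and 0.69 (minor; no effect on the design).

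The cost is protocol wording and table labels. No new patients, visits or procedures are needed.
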